3.4.1 Group sequential design with 2 interim analyses

The planned sample size is a minimum of 254 and a maximum of 508 subjects.

The sample sizes for this trial are calculated using the following assumptions:

- significance level equal to 0.025 (1-sided)
- power of 0.8 (at final analysis)
- allocation ratio of 1:1
- Two interim analyses at half and three-quarter information time (i.e. when half and three-quarter of the subjects are evaluable for response), using spending functions with O'Brien-Fleming-Type boundaries for efficacy and futility.
- Efficacy endpoint (%All in optimal, more is better) on logit-scale:
 - Mean conventional = -1.86
 - Mean INTELLiVENT-ASV = -1.28
 - \circ Sd = 1.5 for both devices
- Safety endpoint (%Any in sub-optimal, less is better) on logit-scale:
 - Mean conventional = -0.09
 - Mean INTELLiVENT-ASV = -0.74
 - \circ Sd = 1.6 for both devices
- Correlation between endpoints = -0.85
- Dropout could occur when subjects are ventilated for less than 24 hours after inclusion because of unexpected death, transfer to another ICU or withdrawal of informed consent. A maximum dropout rate of 5% of these cases is expected. Given the large uncertainty on the assumed performance differences and the inclusion of a sample size reassessment, the initial sample size is not increased to deal with this dropout rate. At the second interim the sample size will be re-estimated, taking this observed dropout rate into account.

The table below shows the sample sizes and characteristics of a study with 2 interim analyses, with O'Brien-Flemming boundaries for efficacy and futility. The final sample size for this group sequential design is 254. 254 stands for the number of subjects with evaluable endpoints and means more subjects might have to be enrolled to reach this number. The p-values for significance are increasing at each analysis while the p-value to stop for futility decreases from the first interim analysis to the final analysis. The study has a high probability to stop at the first interim analysis if both ventilation modes have an equal performance.

Sample sizes and operational characteristics for the trial using O'Brien Fleming boundaries for futility and efficacy.

Analysis	SS	Z	Nominal p	α Spend	end Power	
		Efficacy	Efficacy		(Prob stop H _A)	
1 (IA1)	128	2.96	0.0015	0.0015	0.25	

2 (IA2)	192	2.36	0.0093	0.0097	0.
3 (final)	254	2.02	0.0220	0.0250	0
Analysis	SS	Z	Nominal p	Prob Futility Stop	
		Futility	Futility	(Prob stop under H ₀)	

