3.4.2 Adaptive sample size increase

An adaptive sample size reassessment is foreseen at the second interim analysis. In case promising results are obtained at this interim analysis, additional resources will be committed to the trial. Following Mehta and Pocock (Mehta, 2011), sample sizes will only be increased in case the interim results are promising, in which case the overall type-I error is not inflated by use of the conventional Wald Statistic. The maximum number of additional subjects will be capped at 254 (above the pre-planned 254 subjects) or a maximal total sample size of 508. More specifically, this 'promising zone' is defined in terms of the conditional probability of rejecting the null hypothesis at final analysis, given the estimated performance difference at interim ('conditional power') and assuming that this estimated performance difference is the true underlying difference. Depending on the conditional power (CP) for each of the two endpoints at the second interim analysis, three different zones and anticipated actions are to be considered:

1) **Unfavourable zone**: At least one endpoint with CP < 0.33.

The interim results are so disappointing that it is not worth to increase the sample size to retrieve CP and the original sample size is retained. This zone is defined as 0 to 0.33, for a sample size reassessment at 0.75 information fraction. If the CP for either of endpoints is below 0.33, this is considered unfavourable, and no sample size increase will be performed.

Promising zone: Both endpoints with CP >0.33, at least one endpoint with CP <0.80

If the CP is above 0.33 but below the originally planned 0.80 for at least one primary endpoint, the sample size will be increased by just the right amount to recover the targeted power of 0.80, while not exceeding the pre-specified maximal sample size of 508 subjects. As stated above, both endpoints would need to have a CP above 0.33 and one endpoint a CP below 0.80 to embark on a sample size increase. The sample size increase will be set to the highest of two recalculated sample sizes if both endpoints have a CP between 0.33 and 0.80.

3) Favourable zone: Both endpoints CP >0.80

The conditional power at second interim analysis is 0.80 or larger for both endpoints. In this zone, the interim results are sufficiently favourable that the trial continues to the original sample size without the need to adaptively increase the trial size.

4. General Analysis Definitions

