Data will be expressed by mean±SD or median (interquartile range) depending on the normality of the distribution assessed with Kolmogorov-Smirnov test. Comparisons will use the two sample Z-test on log-transformed primary endpoint variables. P values <0.025 (one-sided) will be considered significant. Bonferroni adjustment will be applied when applicable. Data will be analyzed using SAS (Version 9.4 or higher).

The tables will be created by treatment arm. Listings with individual values will be provided for all data presented in the tables.

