4.2 Planned analyses

- 4.2.1 Interim analyses for Adaptive sample size reassessment
- 4.2.2 Two interim analyses at half and three-quarter information time (i.e. when half and three-quarter of the subjects are evaluable for response), using O'Brien-Fleming boundaries for efficacy and futility.

A Data Safety Monitoring Board will be settled by the sponsor and will be composed of experts in mechanical ventilation independent from the study coordinators and investigators.

The responsibility of the DSMB is to evaluate safety data during the trial and to advise Hamilton Medical about the continuing safety of the Study. Tables, listings and figures to be presented during each DSMB meeting are listed in the DSMB Charter. However, additional items can be added upon request from DSMB members.

Listings of all Adverse Events and Device Deficiencies will be provided by Hamilton Medical to the Independent Medical Monitor to evaluate safety of the study device. All events, including any device related events will be reviewed case by case by the Independent Medical Monitor. A safety concern raised by the Independent Medical Monitor triggers a DSMB meeting. Trial data will be reviewed on a periodic basis as defined in the DSMB Charter.

Based on the available safety data, the DSMB may recommend that Hamilton Medical modify or terminate the trial. DSMB composition, duties, procedures, deliberation rules are detailed and documented in the DSMB Charter.

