7.1 Primary Efficacy Variable

The primary efficacy endpoint is a composite endpoint to assess the ability to keep the ventilation and oxygenation variables in optimal target ranges. The primary efficacy variable will be calculated as the percentage of time spent with **ALL** six variables in the optimal target ranges during the **7 days** after randomization:

- 1) Tidal volume (VT)
- 2) Maximum pressure (Pmax)
- 3) Oxygen saturation measured by pulse oximetry (SpO₂)
- 4) End-tidal partial pressure of carbon dioxide (PetCO₂)
- 5) Respiratory rate (RR) for spontaneous breathing subjects
- 6) Pmax-PEEP for passive ARDS subjects

The optimal and sub-optimal ranges are defined by pertinent guidelines for different clinical conditions including normal lungs, brain injury, ARDS, and chronic hypercapnia.

The primary efficacy variable will be expressed by median (interquartile range). Log transformation will be performed on the data before performing the 2 sample Z-test. Comparisons will use the 2 sample Z-test for log transformed variables. The P values <0.025 (one-sided, the hypothesis is that INTELLiVENT-ASV is better than "non-automated ventilation" on the Hamilton Medical Ventilators, in terms of efficacy) will be considered significant.

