8.2 Primary Safety Variable

The primary safety variable will be calculated as the percentage of time spent with **at least one** of the six variables in the sub-optimal target ranges during the **7 days** after randomization:

- 1) Tidal volume (VT)
- 2) Maximum pressure (Pmax)
- 3) Oxygen saturation measured by pulse oximetry (SpO₂)
- 4) End-tidal partial pressure of carbon dioxide (PetCO₂)
- 5) Respiratory rate (RR) for spontaneous breathing subjects
- 6) Pmax-PEEP for passive ARDS subjects

The primary safety variable will be expressed by median (interquartile range). Log transformation will be performed on the data before performing the 2 sample Z-test. Comparisons will use the 2 sample Z-test for log transformed variables. The P values <0.025 (one-sided, the hypothesis is that INTELLiVENT-ASV is better than conventional non-automated ventilation in terms of efficacy) will be considered significant.

Primary safety variable will be performed on the safety population.

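### The SAP's decision rule tests the co-primary endpoints at one-sided p < 0.025, but its own group-sequential table sets the final cut-off at 0.0220

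*SAP*

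**What the plan says.** The design section makes 0.025 the overall level. SAP 3.4.1 lists "significance level equal to 0.025 (1-sided") among its assumptions. Its table then gives efficacy nominal p of 0.0015 at 128 subjects, 0.0093 at 192 and 0.0220 at 254, with cumulative alpha spend of 0.0015, 0.0097 and 0.0250. The text adds: "The p-values for significance are increasing at each analysis while the p-value to stop for futility decreases". Protocol 10.2, Table 5, carries the same figures.

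The analysis sections use a different number. SAP 4 (General Analysis Definitions) says "P values <0.025 (one-sided) will be considered significant". SAP 7.1, for efficacy, says "The P values <0.025 (one-sided, the hypothesis is that INTELLiVENT-ASV is better". SAP 8.2, for safety, says "The P values <0.025 (one-sided, the hypothesis is that INTELLiVENT-ASV is better than conventional non-automated ventilation". None of the three names a look, cites the table, or says that 0.025 is an overall level.

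The other places where the two could be reconciled do not do so:
- SAP 4.2.2 attaches "using O'Brien-Fleming boundaries for efficacy and futility" to the two interim analyses.
- SAP 4.2.3 (Final Analysis) gives no critical value.
- SAP 4.9 (Changes to Protocol) lists only the site cap.
- Protocol 10.4.5 gives no p-value threshold.

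**The concern.** The interim thresholds are not in doubt, because SAP 3.4.1 and 4.2.2 both apply O'Brien-Fleming boundaries there. The conflict is at the final look. A final one-sided p from 0.0220 up to 0.025 (Z between 1.96 and 2.014) wins under SAP 7.1 or 8.2 and fails under the table.

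Two other parts of the plan depend on the same number. SAP 3.4.2 says of the sample-size increase "in which case the overall type-I error is not inflated by use of the conventional Wald Statistic", which depends on the final critical value. It also defines conditional power as the "conditional probability of rejecting the null hypothesis at final analysis, given the estimated performance difference at interim", so the zone that decides whether the trial is enlarged cannot be computed until one final critical value is fixed.

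The study is described as pivotal and as the primary basis for a pre-market approval application. If the threshold were settled only after the final p-value was known, the choice would look post hoc.

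**Working it through.** **Inputs.** From SAP 3.4.1 and Protocol Table 5: one-sided 0.025; looks at 128, 192 and 254 subjects (planned information 0.50, 0.75, 1.00); efficacy Z 2.96, 2.36, 2.02; interim futility Z 0.44, 1.34; logit-scale differences 0.58 (SD 1.5) and 0.65 (SD 1.6); correlation 0.85 in the direction of benefit. From SAP 3.4.2: promising zone at conditional power 0.33 to 0.80, cap 508.

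**1. Reproduce the table.** The O'Brien-Fleming-type spending function is α(t) = 2[1 − Φ(z₀.₉₈₇₅/√t)].
- Cumulative spend at t = 0.50, 0.75, 1.00 is 0.0015, 0.0097, 0.0250, as printed.
- Solving for the boundaries with futility ignored gives Z = 2.963, 2.359, 2.014 and nominal p = 0.0015, 0.0092, 0.0220. The final value matches; the second look is printed as 0.0093.
- The printed final Z of 2.02 corresponds to p = 0.0217. A p of 0.0220 is Z = 2.014.
- Joint power for both endpoints at 254, with futility acted on, is 0.801 against the stated 0.80.

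**2. Per-endpoint type I error without a sample-size increase.** Recursive integration under the null, interim bounds 2.96 and 2.36. Each cell gives the value at 128/254 and 192/254, then at exact 0.50/0.75.

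| Final critical value | Futility non-binding | Futility always obeyed |
|---|---|---|
| 1.960 (p 0.025) | 0.0276 / 0.0277 | 0.0243 / 0.0242 |
| 2.014 (p 0.0220) | 0.0249 / 0.0250 | 0.0223 / 0.0223 |

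The top-left figure is 0.0015 + 0.0081 + 0.0180 = 0.0276.

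**3. Which futility reading gives 0.0220?** With interim bounds 2.96 and 2.36 at 0.50/0.75, the final bound that spends exactly 0.025 is Z = 2.014 (p 0.0220) if futility is non-binding and Z = 1.939 (p 0.0263) if it is binding. So the printed 0.0220 is the non-binding boundary, and 0.025 is the exact boundary under neither reading.

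**4. With the sample-size increase** (conditional power under the interim trend, 4 million simulated trials per case). A final 1.96 gives about 0.026 non-binding and 0.023 with futility obeyed. A final 2.014 gives about 0.024 and 0.021.

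**5. Both endpoints null, both required to succeed** (non-binding, with the increase): 0.013 for a final 1.96 and 0.011 for 2.014. The figures in steps 2 and 4 are therefore the worst case, where the other endpoint is truly effective.

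**6. How often the choice matters.** With the increase and non-binding futility, a final Z falls between 1.96 and 2.014 in about 0.2% of trials under the null and 0.7% at the planned efficacy effect.

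**7. Promising zone.** With t = 192/254, CP = Φ[(Z₂/√t − c)/√(1 − t)], so Z₂ = √t·[c + √(1 − t)·Φ⁻¹(CP)]. For CP 0.33 and 0.80, c = 1.96 gives Z₂ from 1.52 to 2.07, and c = 2.014 gives 1.56 to 2.11.

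**The case against.** The best reading for the plan is that 0.025 in SAP 4, 7.1 and 8.2 only restates the overall level. The same sentence serves the tertiary endpoints in SAP 7.3 and 8.4, which have no boundary table, so it looks like standard wording. The table sets the final threshold as explicitly as the interim ones, so if it overrides a bare 0.025 at the interims it can do so at the end. That may well be the intent. But the text applies 0.025 to p-values from the Z-test, and an analyst following SAP 7.1 literally would test the final look at 1.96.

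The consequence is also conditional. If futility stops are obeyed, a final 0.025 stays below the nominal level, and the stated 0.80 power fits a design in which futility is acted on. Excess error needs a futility stop overridden, one endpoint null and the other effective. This limits the severity. It does not remove the point, because the documents never say whether futility is binding and the tabulated 0.0220 is the non-binding value.

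The zone edges move by only 0.04 to 0.05 in interim Z, and section 3.4 contains only one tabulated final critical value. That is true, but the conditional-power rule does not say that this is the value to use.

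**Conclusion.** The concern holds. As written, the SAP has two final thresholds for its co-primary endpoints, 0.025 and 0.0220, and no passage chooses between them. With the planned interim boundaries, a final cut-off of 0.025 gives a per-endpoint one-sided error of 0.0276 to 0.0277 without a sample-size increase and about 0.026 with it, if futility is non-binding. There is no excess if futility is always obeyed.

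These figures assume the interim boundaries are applied as tabulated. The both-null figures and the joint power also assume that both co-primary endpoints must succeed. The numerical effect is small and the disputed band is narrow. It should still be fixed, because it sits in the confirmatory decision rule of a pivotal study.

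**What to change.** In SAP 4, 7.1 and 8.2, for the two co-primary endpoints only, replace the bare cut-off with wording such as:

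> The overall one-sided level is 0.025 for each co-primary endpoint. Each look is tested against its O'Brien-Fleming-type boundary in section 3.4.1 (nominal p 0.0015, 0.0093, 0.0220, recomputed from the spending function at the actual information fractions relative to 254). The nominal p governs. The same final critical value is used for conditional power at the second interim analysis and is kept after any sample-size increase.

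Also state whether the futility bounds are binding, noting that the tabulated alpha corresponds to non-binding. The printed final Z can stay if the nominal p governs. If it is reprinted, give three decimals (about 2.014): rounding down to 2.01 gives a type I error of 0.0251 to 0.0252.

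This changes SAP text only, with no change to data collection or planned sample size, and should be done before final results are seen. The price of the stricter threshold, with the increase in place, is:
- Power for both endpoints goes from 0.877 to 0.866 if futility is not applied, or from 0.840 to 0.834 if it is obeyed.
- Power for efficacy alone goes from 0.900 to 0.892, or from 0.871 to 0.865.

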7.2 Secondary Efficacy Variable

Secondary efficacy variables covering physiologic parameters, clinical outcomes, workload, safety events, typical clinical complications up to day 28 after enrolment and associated interventions will be assessed.

Please refer to section 3.2.2 of SAP for the complete list for the secondary efficacy endpoints.

Data will be expressed by median (interquartile range) or mean±SD and 95% confidence interval depending on the normality of the distribution assessed with Kolmogorov-Smirnov test. Between group differences will be performed using the 2 sample Z-test for normal variables or Mann-Whitney test for variables with a non-normal distribution. If applicable, a Bonferroni correction will be applied for pairwise comparisons corresponding to the sponsor's variable of interest.

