Ventilatory parameters manual assessment		X	X	X	X	X	X	X	X	X	X	X	X	X	X	X
24h Recording of ventilation parameters *(Memory Box)		X	X	X	X	X	X	X	X	X	X	X	X	X	X	X
Blood gas analysis (If available visit $\pm 2h$)	X	X#	X	X	X	X	X	X	X	X	X	X	X	X	X	X
ICU severity Scores (SAPS II, APACHE II)					X											
SOFA score						X			X			X				X
Concomitant sedation, analgesia and myorelaxants use		X	X	X	X	X	X	X	X	X	X	X	X	X	X	
Concomitant vasopressors and inotropics use		X		X	X	X	X	X	X	X	X	X	X	X	X	

Study Period	Intervention Period														End of Study	Study Exit
	Time	Day 0	Screening	Baseline	Day 0	Day 0	Day 1	Day 1	Day 2-3	Day 4	Day 4	Day 5-6	Day 7	Day 7	Day 8-27	
Time specifications		T0	T0+1h	T0+6h (only if T0 before 12 a.m.)		morning visit time + at least 6h			mornig visit time + at least 6h			morning visit time + at least 6h			Day XX	Day 28
Visit #	Visit 1	Visit 2	Visit 3	Visit 4	Visit 5	Visit 6	Visit 7-10	Visit 11	Visit 12	Visit 13-16	Visit 17	Visit 18	Visit 19-59	Visit 60	Visit 61	
Number of recruitment maneuvers within the last observation period				X	X	X	X	X	X	X	X	X	X	X		
Concomitant rescue therapies (proning, Nitric oxyde, ...)		X		X	X	X	X	X	X	X	X	X	X	X		
Weaning information NIV, CPAP, High Flow.)				X	X	X	X	X	X	X	X	X	X	X		
Screening of readiness to extubate criteria (SBT)						X	X	X	X	X	X	X	X	X		
Assessment of re-intubation status							X	X	X	X	X	X	X	X		
Extubation failure (yes/no)							X	X	X	X	X	X	X	X		
Acute Kidney Injury (AKI) status and need vor RRT (yes/no)	X	X						X		Xf	X			Xf	X	X
Criticall illess polyneuro- myopathy status (yes/no)	X	X						X		Xf	X			Xf	X	X
Criticial illess encepaehlopathy status (yes/no)	X	X						X		Xf	X			Xf	X	X
Tracheostomy status (yes/no)											X			Xf	X	X
Resuscitated cardiac arrest status (yes/no)								X			X					X
Other imminently life-threatening experience								X			X					X
Barotrauma status (yes/no)								X			X					X
Rescue therapy requirement (APRV, HFO, ECCO2R and ECMO).																X
Patient status incl. Withhold of weaning and/or withdrawald of MV															X	X**
Ventilation duration for study period (if reintubated beyond 48h)															X	
ICU and hospital length of stay															X	X**
ICU/Hospital death															X	X**

Study Period	Screening	Baseline	Intervention Period												End of Study	Study Exit
			Day 0	Day 0	Day 0	Day 1	Day 1	Day 2-3	Day 4	Day 4	Day 5-6	Day 7	Day 7	Day 8-27	Day XX	Day 28

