Physiology admission scores SAPS II, APACHE II and SOFA, Mechanical ventilation characteristics (INTELLiVENT-ASV, VC, PAC, VAC, SIMV, BiPaP, APRV, PS, ASV, Others) and Arterial Blood Gas analysis (PH, PaO₂, PaCO₂, HCO₃⁻, SaO₂, FiO₂, End-Tidal CO₂) at baseline will be summarized by treatment arms. Similarly, stratification information based on subject condition at inclusion will be tabulated by treatment arm if applicable. In addition, baseline characteristics will be presented by region (US vs EU). For categorical baseline variables, Fisher exact test will be used to test if there's a significant difference between US and EU whereas for continuous variables Mann-Whitney U test will be used to test for differences between the two populations. Results for these statistical tests will be mainly for informative purpose and no inference is intended to be made on these results.

7. Efficacy Evaluation

Efficacy evaluation will be performed on the ITT population. Values for optimal, acceptable, and sub-optimal ranges (maybe different for passive and spontaneous breathing ventilation periods) are listed in Values for optimal, acceptable and sub-optimal ranges of the study protocol.

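### SAP 7.2 compares PaO2/FiO2 and FiO2 between arms without using the blood gas taken before the allocated mode starts: a valid analysis, but one that gives up precision

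*SAP*

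**What the plan says.** SAP 3.2.2 and Protocol 5.2 name PaO2/FiO2 and FiO2 among the secondary physiologic endpoints, recorded up to day 28. For all secondary efficacy variables SAP 7.2 states: "Between group differences will be performed using the 2 sample Z-test for normal variables or Mann-Whitney test for variables with a non-normal distribution". A Bonferroni correction may follow, but there is no adjustment for a baseline value.

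A baseline value is planned. In Protocol Table 1, repeated in SAP Appendix 1, the row that begins "Blood gas analysis (If available visit" is marked at screening (Visit 1). It is marked again at baseline (Visit 2), with a footnote limiting that repeat to subjects whose ventilator settings changed in between. SAP section 6 includes PaO2 and FiO2 in the arterial blood gas set, which "at baseline will be summarized by treatment arms". SAP 4.6 assumes that baseline assessments made on the day of ventilation come before study ventilation.

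The only covariate-adjusted treatment comparison in the SAP is in 7.4: an ANCOVA of the primary efficacy variable, adjusted for region, as a sensitivity analysis. The covariates in SAP 4.8 serve imputation only and do not include baseline PaO2/FiO2 or FiO2.

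**The concern.** A subject's oxygenation before the allocated mode starts is likely to predict oxygenation afterwards. When an outcome has its own pre-treatment value, a two-sample test leaves the predictable part of the between-subject variation in the error term. Any chance difference between arms at baseline also stays in the estimate.

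The endpoints are not incidental. Oxygenation control is one of the three listed device features (Protocol 3.1), the rationale cites harm from unnecessarily high FiO2 (Protocol section 3), and the synopsis says the results will support a pre-market application. No power is stated for these endpoints, so there is reason to use precision that is already available.

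The point is confined to these two secondary endpoints and their own baseline values. It does not touch the co-primary tests.

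**Working it through.** **1. The plan's own figure.** The only stated power is for the co-primary endpoints: 0.80 at 254 evaluable subjects, one-sided alpha 0.025, "allocation ratio of 1:1". Inputs from SAP 3.4.1 (logit scale):

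- Efficacy: "Mean conventional = -1.86" and "Mean INTELLiVENT-ASV = -1.28", so the difference is 0.58, with SD 1.5.
- Safety: −0.09 and −0.74, so the difference is 0.65, with SD 1.6.
- Correlation between the endpoints: −0.85.

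Fixed design, n per arm = 2(1.960 + 0.842)² SD²/difference²:

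- Efficacy: 2 × 7.85 × 2.25/0.3364 ≈ 105 per arm, 210 in total.
- Safety: 2 × 7.85 × 2.56/0.4225 ≈ 95.1, rounded up to 96 per arm, 192 in total.

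Simulating the three looks (128, 192, 254) with the tabulated efficacy and futility bounds gives power 0.836 for efficacy alone, 0.871 for safety alone and 0.800 for both together. The stated 0.80 is reproduced, and nothing below alters it.

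**2. What adjustment would do.** With rho the within-arm correlation between the baseline value and the outcome, large-sample ANCOVA gives:

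- adjusted variance of the treatment difference = unadjusted variance × (1 − rho²)
- power = Φ(2.802/√(1 − rho²) − 1.960), for a difference that the unadjusted test would detect with power 0.80
- unadjusted sample size with equal precision = 254/(1 − rho²)

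The documents give neither rho nor a power for these endpoints. Both rho and the 0.80 starting power are therefore assumptions.

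| rho | variance reduction | power (from 0.80) | equivalent unadjusted N |
|---|---|---|---|
| 0.2 | 4% | 0.816 | 265 |
| 0.3 | 9% | 0.836 | 279 |
| 0.5 | 25% | 0.899 | 339 |
| 0.7 | 49% | 0.975 | 498 |

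Example at rho 0.5: 2.802/0.866 − 1.960 = 1.275, and Φ(1.275) = 0.899. A gain of 5 power points needs 2.802/√(1 − rho²) = 1.036 + 1.960, so rho is about 0.35.

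**3. Missing baseline gases.** The table assumes that every subject has a baseline gas. If only a share p has one and the rest carry a missing-baseline indicator, the reduction is roughly p × rho². The documents give no p. With p = 0.7 as an illustration, the four reductions become 2.8%, 6.3%, 17.5% and 34.3%.

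**4. Which value comes before the allocated mode.** Protocol 8.1.2 starts ventilation recording once randomisation is complete and the allocated mode is selected, so Memory Box data cannot supply a baseline; the blood gas can. Table 1 marks Memory Box recording at Visit 2, so a Visit 2 gas may have been drawn under the allocated mode. The SAP 4.6 ordering is an assumption, and a time stamp would settle it for each subject.

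**The case against.** The strongest reply is that nothing here is an error. Two-sample tests are valid and unbiased under randomisation, and the plan claims no power for these endpoints. That stands: the point is about efficiency.

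Second, randomisation is stratified by clinical condition and site, which limits imbalance between, say, normal lungs and ARDS. Baseline PaO2 and FiO2 are tabulated by arm, so an imbalance would be visible. Both are true. However, ARDS is one stratum although Protocol 8.3.1 sets different oxygenation targets by ARDS severity, and the SAP 7.2 tests use neither the strata nor the baseline value. A visible imbalance would still not be corrected.

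Third, the baseline is weaker than it first appears. The gas is taken only if available. FiO2 at Visit 1 itself is inferred from the baseline gas list in SAP section 6. Under Protocol 8.1.2 a patient may consent before intubation, so a screening gas may not reflect invasive ventilation. FiO2 is set by the controller in one arm and by clinicians in the other, so its earlier value may predict poorly, and differently by arm. All of this reduces the gain. It does not make adjustment harmful: with 1:1 allocation, a common-slope ANCOVA does not lose large-sample precision even if the slopes differ.

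A reader might infer that most of the between-subject variance in later PaO2/FiO2 is avoidable noise. That would need rho² above 0.5, so rho above about 0.71, and the documents give no correlation at all.

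**Conclusion.** The point holds as an optional improvement. For PaO2/FiO2 and FiO2 the plan collects a blood gas before the allocated mode and then leaves it out of the comparison. The variance of the treatment difference could fall by up to 4% to 49% for rho from 0.2 to 0.7. These are upper bounds: they assume a baseline gas in every subject, they shrink with the missing share, and they probably overstate the gain for FiO2. The direction follows from the documents; the size rests on an assumed rho.

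The documents do not support reading this as a biased analysis, as a shortfall in the trial's stated power, or as a fault in the co-primary tests.

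**What to change.** Add to SAP 7.2: PaO2/FiO2 and FiO2 will be analysed by ANCOVA, or rank ANCOVA if non-normal, with arm and the subject's last blood-gas value documented before the allocated mode was started as covariate. That is the Visit 1 value, or the Visit 2 repeat only where its time stamp precedes the allocated mode. Subjects with no such value stay in the model through a missing-baseline indicator. Keep the outcome summary and the observation window as planned, so that the endpoint itself does not change.

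The cost is a few lines of SAP text, a standard model, about one degree of freedom for the covariate and one for the indicator, and a check of gas times against the start of the allocated mode. No new data are needed, and the sample size, alpha and co-primary tests are untouched. SAP 10.1 lists the physiologic-parameter tables for both interim analyses, so the wording should be fixed before anyone drafting it has seen results by arm.
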